9.6 Data Collection

We will collect and enter all patient-reported data electronically using Research Electronic Data Capture (REDCap). The REDCap Survey is a tool for building and managing online surveys. Vanderbilt University, in collaboration with a consortium of institutional partners, has developed this software and workflow methodology for electronic collection and management of research and clinical trial data. Our research team has extensive experience using REDCap and will create and design the surveys in a web browser, with institutional information technology support. The REDCap Survey system offers secure, HIPAA compliant, web-based applications that provide an intuitive interface for participants to enter data, with real-time validation rules at the time of entry.

Participants will be e-mailed (Appendix U) a remote access to the REDCap system containing questionnaires for them to complete or they can complete questionnaires during in-person clinic visits. If

PROTOCOL TITLE: Randomized Trial of a Positive Psychology Intervention for Patients with Hematologic Malignancies Undergoing Hematopoietic Stem Cell Transplantation

any participants refuse or are unable to complete the questionnaires on the computer, they will be permitted to use hard-copy paper versions of the questionnaires. Participants will also be provided the option to complete questionnaires over the phone. The CRC will contact participants (in person or via telephone) daily for two days to remind them to complete and return the surveys. If study participants fail to complete the surveys within seven days of the expected time point, we will report the data as missing and document the reason for incompleteness. Table 4 details the schedule for administering the self-report measures. At enrollment all participants will be mailed the *Actigraph GT3X+* (together with instructions (Appendix V) on how to use the *Actigraph*) for 7 days of wear; minimum acceptable use is 4+ days with 10+ hours of recorded data around day 85-95 post-transplant and prior to the intervention initiation around day 100 post-transplant. After baseline physical activity data collection, participants will mail back the *Actigraph* in prepaid envelopes we will provide. In addition to the *Actigraph*, participants will also be mailed the MEMS Cap (together with the instructions (Appendix W) on how to use the MEMS Cap) for medication (immunosuppressant) adherence assessment over the entire duration of the intervention starting at the time of baseline surveys around day 85-95 post-transplant. All participants will complete baseline assessments approximately 85-95 day post-transplant. All participants will then complete follow-up assessments at Week-9 (with a 1 week window) and at Week-18 (+/- 1 week window) of intervention initiation.

Table 4: Administration of Self-Report Measures

Participant	Baseline	Week-9 (+ 1 week window)	Week-18 (+/- 1 week window)
Patient Measures:			
Demographics	X		
FACT-BMT	X	X	X
PROMIS-Fatigue 8a	X	X	X
PROMIS-PF-20	X	X	X
HADS	X	X	X
PCL (PTSD)	X	X	X
LOT-R	X	X	X
PANAS	X	X	X
GQ-6	X	X	X
SWLS	X	X	X
Flourishing Scale	X	X	X
Brief Cope	X	X	X
MARS-5	X	X	X
SSEQ	X	X	X
Accelerometer	X	X	
MEMS-Cap		Longitudinal from baseline through week 9	

9.7 Overview of Research Procedures

Initial/Enrollment phone call: During this initial approach at a routine outpatient follow-up clinic or phone call, the study procedures will be explained to potential participants. Those who are interested will be screened for eligibility and, mailed or e-mailed a copy of the study information

PROTOCOL TITLE: Randomized Trial of a Positive Psychology Intervention for Patients with Hematologic Malignancies Undergoing Hematopoietic Stem Cell Transplantation

sheet. We will then call patients upon receipt of the information sheet approximately seven days from receipt of the information sheet for enrollment and written consent procedures during a routine clinic visit or verbal consent procedures over the phone. Consented participants will then be randomized to usual care or the intervention group. All participants will be mailed (or given in person at a routine follow-up visit) the electronic pill bottle (MEMS Caps), and the accelerometer (Actigraph GT3X+, small half-dollar sized device that clip on to a belt with no visible readout thus preventing independent subject access to data) to wear for 7 days prior to the intervention initiation in the control group. Participants in the intervention group will also be mailed the study intervention manual together with their accelerometer and electronic pill bottle. At the time of the baseline survey and prior to the start of the intervention, adequate accelerometer wear (at least 4 days with 10+ hours per day worn) will be confirmed. Participants in the intervention group will also be mailed the study intervention manual. Those who have not completed sufficient wear of the device will be asked to re-wear the device until there is sufficient baseline data available.

Baseline Assessments: Around the time of each participant's routine 85-95-day post-transplant routine clinic visit, participants will be asked to complete baseline assessment questionnaires either in person during a routine follow-up visit in clinic, over phone, or via a REDCap survey link that will be e-mailed to participants.

After completion of the baseline survey and a returned accelerometer with adequate data, the interventionist will review the mailed treatment manual with weekly PP exercises to those in the intervention group. Participants in the intervention group will be assigned the first exercise (gratitude for positive events) in preparation for their first phone session.

Weekly phone sessions for positive psychology intervention: Participants in the intervention group will be asked to complete the 9 weekly PP exercises and to speak with the interventionist weekly. Weekly phone sessions will last approximately 15-20 minutes. Prior to completing each phone session, participants will be asked to rate their current level of happiness and optimism, using a 10-point Likert scale. Immediately after completing the exercise and phone session, participants will rate the ease of exercise/session completion, overall utility of the exercise/phone session, and their current levels of happiness and optimism, all using 10-point Likert scales. These calls will be recorded using the SONY IC Recorder ICD-PX370 so that a percentage (10%) of these recordings can be reviewed by [name], to ensure that the PP intervention is being delivered as described in the protocol. Given the results of our prior PP studies in medical populations yielding a 64-85% completion rate of the exercises, our recent proof-of-concept trial (18-225) yielding 100% completion rate in this population, and given that this is a feasibility study (i.e., we want to assess participants' willingness to complete the phone sessions), we will expect participants to complete at least 6 PP exercises. In other words, if a participant completes at least 6 sessions, missed sessions will not be considered a deviation from the protocol.

All participants will receive a \$50 check after completion of the intervention. Participants in the usual care group will also receive a \$50 at the same timepoint. All participants (in either the usual care group or intervention group) who complete 18-week follow-up assessments will receive an additional \$50 check.

PROTOCOL TITLE: Randomized Trial of a Positive Psychology Intervention for Patients with Hematologic Malignancies Undergoing Hematopoietic Stem Cell Transplantation

Follow-up assessments: During Week 8 of the intervention, all participants (those in the intervention group and the usual care group) will be mailed (or given in-person during a routine follow-up clinic visit) an accelerometer to wear for 7 days in order to assess physical activity at follow-up. Then, at Week 9, participants will return the accelerometer and MEMS Cap, and will repeat self-assessment questionnaires obtained at the beginning of the study either in-person during a routine follow-up clinic visit, over the phone, or via a REDCap survey link e-mailed to them, depending on participant's preference. Furthermore, participants in the intervention group will be asked to provide feedback about the program via a recorded exit interview over the phone.

Positive Psychology Program Content: All phone sessions will include (a) a review of the ease and utility of the week's PP exercise, (b) a discussion of the rationale of the next week's PP exercise through a guided review of the PP manual, and (c) assignment of the next week's PP exercise. During the calls, the interventionist and participant will also review the next section of the treatment manual and prepare for the upcoming week's exercise.

9.8 *Procedures performed to lesson the probability or magnitude of risks*

We will ensure that contact with participants is confidential by using only the phone numbers and other contact information that are specifically allowed by the participants. We will not leave study-related messages for participants unless expressly allowed by participants. Upon enrollment, we will ask all participants for the preferred times for calls and if it is acceptable to leave voice messages on their phones. We will adhere to any and all patient requests regarding contact.

Digital recordings of the sessions and exit interviews will be completed using portable recorders. If a study participant were to refuse audio recordings, they can either remove themselves from the study or work with the study staff to choose an alternative to audio recording such as transcription. All recordings will be downloaded immediately from the recorders and the electronic files will be kept within the firewalled, password-protected file on a Partners/Mass General Brigham/DFCI server. Recordings will contain minimal personally identifiable information as the recordings will include the participant's voice but their names or other identifying information on the recordings will not be used and will be erased following review.

All data regarding the objective adherence devices will be encoded only with the study participant number that is linked to personal identifying information in the study database. The devices will not be marked with any personal identifiable information, and the database that will be used to monitor medication adherence and accelerometer data will only contain participant numbers. Data that is uploaded from each participant's accelerometer will be coded without identifying information and will be accessed from a locked computer in a research team office.

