5.0 Study-Wide Recruitment Methods

5.1 Recruitment and Enrollment Procedures:

Prior to study start, the PI will present at the DFCI HSCT protocol meeting to inform the HSCT clinicians about the study and to alert them to the screening, recruitment, and enrollment procedures. The CRC will screen the DFCI HSCT clinic database to recruit, screen, and identify potentially eligible patients. The CRC will then email the transplant oncology clinician to notify them that the patient is potentially eligible for study participation and to inquire about any concerns regarding their study participation (Appendix C). If the treating transplant clinician has any concerns regarding a patient's study participation, then the CRC will document the reason and not approach that individual. If there is no concern regarding study participation, the CRC will approach patients for study participation as they approach their 70-80-day post transplant recovery milestone over the phone or in clinic and ask if they are interested in participating (Appendix D). Patients will only be contacted twice over the phone and will be provided with a call back number to either opt-in or opt-out of the study. Interested participants will be screened with the BIMS and provided (in-person at clinic, mailed or e-mailed) an information sheet of the study to review prior to their completing consent procedures. Patients will have the option of enrolling in the study in-person at the patient's scheduled clinic visit or over the telephone with a

PROTOCOL TITLE: Randomized Trial of a Positive Psychology Intervention for Patients with Hematologic Malignancies Undergoing Hematopoietic Stem Cell Transplantation

verbal consent (Appendix E) seven days after receiving the study information sheet. Consented participants will then receive an *Actigraph GT3X+* and MEMS Cap for baseline (Day 85-90 post-HSCT) physical activity and medication adherence assessment, respectively. Additionally, consented participants will complete baseline assessments around Day 85-90 post-HSCT.

Participants who provide verbal consent will be asked to sign HIPAA Authorization to review their medical records for the purposes of research. HIPAA authorization maybe provided at a clinic visit or remotely over e-mail or via mail in the setting of the COVID-19 stipulations. Participants who complete written informed consents will sign a HIPAA authorization as part of the written informed consent.

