Participants will be registered with the Clinical Trials Management System after they have consented, provided baseline *Actigraph GT3X+* data, and completed baseline assessments. If participants provide consent but do not complete baseline Actigraph data collection and assessments, they will not count towards accrual numbers. Participants who withdraw from the study or die during the study period will not be replaced and they will count towards accrual numbers.

DF/HCC institutions will register eligible participants in the Clinical Trials Management System (CTMS) Oncore as required by DF/HCC SOP REGIST-101. Registration must occur after the initiation of protocol-specific procedures or assessments.

For registration of participants from the DF/HCC institutions, study staff will complete the DF/HCC protocol-specific eligibility checklist. Study staff will confirm that the participant meets all inclusion criteria as described in this protocol. Study staff will then register study participants through OnCore. Study staff will follow DF/HCC Standard Operating Procedure for Human Subject Research Titled *Subject Protocol Registration* (SOP #: REGIST-101) and register the participant on the protocol.

Once the patient has been registered, a member from the MGH Cardiac Psychiatry Research Program (CPRP) team or the Cancer Outcomes Research and Education Program (CoRE) (independent from the study staff) will perform randomization procedures using a computer-generated randomization schema, stratified by GVHD status.

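### Sections 9.7 and 5.1 give opposite orders for randomisation and baseline; under 9.7 the baseline follows allocation, and randomised patients without baseline data drop out of accrual

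*Combined protocol and SAP*

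**What the plan says.** Section 9.7 describes consent and continues: "Consented participants will then be randomized to usual care or the intervention group". It then sends the devices to everyone and adds: "Participants in the intervention group will also be mailed the study intervention manual together with their accelerometer and electronic pill bottle". The check of accelerometer wear comes next, and there the manual is mailed a second time: "will be confirmed. Participants in the intervention group will also be mailed the study intervention manual. Those who have not completed sufficient wear". The questionnaires come last: "Around the time of each participant's routine 85-95-day post-transplant routine clinic visit, participants will be asked to complete baseline assessment questionnaires". Once the survey is done and the accelerometer is back with adequate data, the interventionist goes through a manual that has already been mailed.

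Section 5.1 gives another order. Consented patients receive the accelerometer and "MEMS Cap for baseline (Day 85-90 post-HSCT) physical activity and medication adherence assessment, respectively". Then: "Participants will be registered with the Clinical Trials Management System after they have consented, provided baseline" Actigraph data and completed the baseline assessments. Randomisation, by someone independent of the study staff, follows registration. Patients who consent but do not complete baseline are left out of the accrual count.

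Section 21.0 also registers after the baseline questionnaires and then randomises, but sets no accelerometer condition.

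The Aim 2 analysis in Section 10.1 centres on the time-by-group interaction, that is, change from baseline. Aim 3 models change over time in activity and adherence. The missing-data paragraph adopts intention-to-treat with everyone randomised.

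**The concern.** In a trial against usual care with no participant blinding described, a baseline measured before allocation cannot be influenced by knowledge of the arm. Section 5.1 protects this and Section 9.7 does not. A PATH patient who receives the manual in the same parcel as the accelerometer knows the allocation while wearing the device and while rating mood, optimism, affect and quality of life. Section 9.7 does not say when usual-care patients are told.

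Two things are at stake. One is the meaning of baseline in the Aim 2 and 3 contrasts, whose effect sizes are to inform the size of a later trial. The other is who belongs to the trial: an accrual rule that excludes patients without baseline data is harmless if they have not yet been randomised, but not if they have.

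**Working it through.** **Step 1: the orders side by side.**

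- Section 9.7: consent, randomisation, devices (with the manual for PATH), wear check, baseline questionnaires, review of the manual.
- Section 5.1: consent, devices, baseline accelerometer data and assessments, registration, randomisation.
- Section 21.0: baseline questionnaires, registration, randomisation. It nevertheless lists the manual for randomised PATH patients ahead of the baseline survey link, without a date.
- Section 18.1: lists the manual in the same position, also undated.
- Section 9.1: mentions the manual after the baseline questionnaires, which is compatible with 5.1.

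Sections 9.7 and 5.1 place randomisation on opposite sides of baseline. The repeated manual sentence makes 9.7 unclear about the mailing, but its randomisation sentence still precedes baseline.

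**Step 2: does anything decide between them?** No clause ranks the sections. Sections 18.1 and 21.0 both refer to 5.1 for recruitment procedures, and the two sections that say who randomises (5.1 and 21.0) place it after registration. The registration wording is less settled. Section 5.1 puts registration after protocol-specific procedures begin, 21.0 puts it before, and 3.1 puts it before only when an institutional procedure requires it. That procedure is not in the documents. This matters here only because registration triggers randomisation.

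**Step 3: which baselines are affected under 9.7?** Table 4 lists 13 questionnaires besides demographics, all given at baseline, week 9 and week 18. With the accelerometer, these are the affected measures. The electronic pill bottle is not included: Sections 9.1 and 9.6 start it at or after the baseline surveys, so it has little or no pre-allocation period in either order.

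**Step 4: effect on the change contrasts.** Let δ be the true effect, x the between-arm baseline shift caused by knowing the arm, and k the share of x still present at follow-up.

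- Order of 5.1 (clean baseline): estimate = δ + kx, error = kx.
- Order of 9.7: estimate = δ + kx − x, error = −(1 − k)x.
- Difference, 9.7 minus 5.1: (δ + kx − x) − (δ + kx) = −x, for every k.

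The documents give neither x nor k, so neither size nor direction can be calculated.

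**Step 5: accrual and analysis sets.** Section 5.1 counts towards the 70 (35 per arm) only patients with baseline data. Under 9.7, suppose m further PATH patients are randomised and never complete baseline. Section 9.7 assigns them no exercise, since that requires a completed survey and adequate accelerometer data. With c patients completing at least 6 of 9 exercises:

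- Accrual rule of 5.1: c/35.
- Denominator of Section 1.2 (all randomised to the intervention): c/(35 + m), which is smaller whenever c and m are above zero.
- Denominator of Section 10.1 (those who start the intervention): these m patients are excluded.

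Intention-to-treat in 10.1 includes them. The documents give no value for m. Under the 5.1 order m is zero by construction.

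**The case against.** The strongest reply is that 9.7 is an overview, that it mails the manual twice and so is loosely drafted, and that the documents lean towards 5.1. This stands as far as intent goes. It does not remove the conflict, because 9.7 is explicit about sequence and a coordinator working from it would randomise at consent. Section 9.7 also has patients re-wear the accelerometer until the data suffice, which should keep m small but does not cover questionnaires never completed.

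A reader might infer four stronger points that the documents do not support.

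- **That treatment effects would be biased by a known amount.** Any figure for x would be assumed.
- **That the 5.1 order is always closer to the truth.** By Step 4, if k exceeds 0.5, the 9.7 estimate is nearer δ. The 5.1 order is the natural reference if expectancy present at follow-up counts as part of the effect of assignment, or if little of the shift persists. The plan says neither.
- **That allocation precedes baseline by a definite number of days.** Section 5.1 says only that "the CRC will approach patients for study participation as they approach their 70-80-day post transplant recovery milestone over the phone or in clinic", with consent "seven days after receiving the study information sheet". The baseline window is day 85-90 in Sections 5.1, 18.1 and 21.0, but day 85-95 in 9.1, 9.6 and 9.7. Only the order is firm.
- **That a baseline shift biases the primary endpoint.** Exercise completion and the ease and utility ratings use no baseline value. Nor do the session-level GEE or the Wilcoxon tests at weeks 9 and 18. The primary aim is touched only through its denominator.

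**Conclusion.** The contradiction is certain from the text; its consequences depend on 9.7 being followed. In that case the 13 questionnaires and the accelerometer have no pre-randomisation baseline, and the Aim 2 and 3 change contrasts could move by an unknown amount in either direction. This assumes that PATH patients recognise their allocation from the manual. Those contrasts are exploratory: Section 10.2 promises only tentative effect sizes, and Section 10.1 also checks the next trial's size against a clinically meaningful difference.

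The second consequence needs no assumption about psychology. Any patient randomised without baseline data would be outside accrual, inside the intention-to-treat set, and treated differently by the two feasibility denominators. The documents do not show which order is used in practice, so it cannot be concluded that baselines were in fact collected after allocation. The case for amending is that the problem is systematic and cheaply avoided, not that it is shown to be large.

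**What to change.** Adopt the sponsor's own 5.1 order throughout.

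- **Section 9.7:** have randomisation, disclosure of the arm and release of the manual follow completed baseline questionnaires and confirmed accelerometer wear. Delete the phrase that ties the manual to the device mailing, and keep one manual sentence, placed after randomisation.
- **Sections 18.1 and 21.0:** move the manual sentence after randomisation, and add the accelerometer condition to 21.0.
- **Registration wording (3.1, 5.1, 21.0):** make completed baseline, not registration alone, the stated condition for randomisation, so that the inconsistent registration sentences cannot trigger it earlier.

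The cost is amendment wording, a separate manual mailing to about 35 participants, and a slightly tighter interval before the first session at about day 100. Section 9.7 already waits for adequate accelerometer data before assigning the first exercise, so the added time is that of registration, randomisation and posting.
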